4.6 Microbiologically Evaluable (ME)

All patients included in both the m-mITT and CE populations at the EOT visit (ME-EOT), and at the TOC visit (ME-TOC) and meet the following criteria are microbiologically

evaluable:

a) Have an appropriately collected urine culture specimen and interpretable urine culture result at the EOT and TOC visits, respectively.

b) Had a microbiologic assessment of eradication or persistence (and not indeterminate) at the EOT or TOC visits, respectively.

4.7 Determination of Inclusion in Analysis Populations

Inclusion into the ITT, MITT, m-MITT and Safety populations will be determined programmatically from the electronic case report form (e-CRF) data. Inclusion into the CE populations will be determined programmatically from the e-CRF data and through a manual review conducted by the sponsor. The sponsor will review both clinical and microbiological data for determination of criteria used to assess inclusion in the CE populations and for determination of baseline and post-baseline pathogens. The sponsor will review the data concurrent with the conduct of the study. Inclusion into the ME populations will be determined programmatically.

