5 DEFINITION OF OUTCOME MEASURES

5.1 Primary Efficacy Outcome Measure

The primary efficacy outcome is overall response assessed on Day 12 (+/- 1 day) in the m-MITT using the definitions listed below.

A patient will be programmatically defined as a responder based on the following:

- The patient is alive;
- The patient has received no rescue therapy for uUTI (if an antibiotic active against the urinary tract pathogen is given for other reasons, then the patient will be considered indeterminate, and analyzed as a non-responder);
- The patient has resolution of the symptoms of uUTI present at trial entry and no new uUTI symptoms, on Day 12 (+/- 1 day);
- Urine culture taken on Day 12 (+/- 1 day) demonstrates <10³ CFU/mL of the baseline uropathogen;

A patient will be defined as a non-responder if at least one of the following criteria is met:

- The patient has died:
- The patient has received rescue therapy for uUTI (If an antibiotic active against the urinary tract pathogen is given for other reasons, then the patient will be considered indeterminate, and analyzed as a non-responder for uUTI);
- The patient has no resolution or worsening of the symptoms of uUTI present at trial entry and/or with new uUTI symptoms;
- Urine culture taken demonstrates $\geq 10^3$ CFU/mL of the baseline uropathogen;

All other patients will be considered indeterminate, including those with missing data needed to determine if the patient is a responder or non-responder. For example, if either urine culture or uUTI symptoms are not completed, the patient will be considered an indeterminate.

For the ITT and m-MITT populations, the proportion of ITT or m-MITT patients with a responder is defined using the following formula:

Number of responders

Number of responders + Number of non-responders + Number of indeterminates

By definition, patients in the CE and ME populations must have sufficient information for determination of efficacy response. Thus, the proportion of CE and ME patients is defined using the following formula:

Number of responders + Number of non-responders

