7.9 Protocol Deviations

A listing of all protocol deviations will be provided. Deviations will also be reviewed by the Sponsor and categorized into general categories such as: inclusion/exclusion criteria, study drug administration, informed consent, visit schedule, test and procedures and other. Protocol deviations will be classified as major, minor or not a deviation. Also, protocol deviations that impact the analyses will be marked by the clinical team and will be excluded from the clinically evaluable population. The number of patients with at least one protocol deviation and the number of patients with at least one deviation in each category will be presented.

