Appendix 3 - Organisms considered as Uropathogens

For the purpose of this study, the following organisms will always be considered a uropathogen when isolated from an acceptable urine culture specimen:

- Monomicrobial or polymicrobial infections caused by:
 - Enterobacteriaceae
 - Enterococci
 - Pseudomonas aeruginosa
 - Staphylococcus. saprophyticus

The m-MITT population for this study will only include patients with UTIs caused by Enterobacteriaceae and/or *S. saprophyticus*.

- Even if the organism was isolated from an acceptable urine culture specimen, the following are never a pathogen:
 - Corynebacterium spp.
 - S. epidermidis
 - S. aureus
 - Bacillus spp.
 - Diphtheroids
 - Micrococcus spp.
 - Lactobacillus spp.
 - Viridans Streptococci
 - Group B Streptococci
 - Gardnerella vaginalis
 - Neisseria gonorrhoeae
 - Yeasts

All isolates not defined above will be assessed on a case-by-case basis via manual review by the Sponsor.

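### Sponsor decisions on evaluability and pathogens are neither kept blind to response nor frozen: CE and ME rates are exposed, the primary m-MITT rate only narrowly

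*SAP*

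**What the plan says.** The primary analysis is fixed in SAP 5.1: "The primary efficacy outcome is overall response assessed on Day 12 (+/- 1 day) in the m-MITT using the definitions listed below".

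SAP 4.7 then describes two ways of deciding who is analysed:

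- For the primary population: "Inclusion into the ITT, MITT, m-MITT and Safety populations will be determined programmatically from the electronic case report form (e-CRF) data".
- For the clinically evaluable populations: "Inclusion into the CE populations will be determined programmatically from the e-CRF data and through a manual review conducted by the sponsor".

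On what the sponsor looks at, it says: "The sponsor will review both clinical and microbiological data for determination of criteria used to assess inclusion in the CE populations". The same sentence extends that review to deciding which baseline and post-baseline isolates are pathogens. On timing: "The sponsor will review the data concurrent with the conduct of the study". Protocol 5.1 describes the study as non-randomized and open label.

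Four other places matter:

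- **Deviations.** Protocol 9.2 left the meaning of an important deviation to the SAP. SAP 4.5(b) leaves it to the clinical team, and SAP 7.9 says "protocol deviations that impact the analyses will be marked by the clinical team and will be excluded from the clinically evaluable population". Neither gives criteria.
- **ME population.** SAP 4.6 requires membership of both m-MITT and CE.
- **Baseline laboratory rule.** SAP 6.4 ranks central over local results in a written order and so fixes baseline pathogen, susceptibility and ESBL status. It covers baseline only.
- **Organism lists.** SAP Appendix 3 lists organisms that always count and organisms that never count as uropathogens, and limits m-MITT to infections caused by Enterobacteriaceae and/or *S. saprophyticus*. For the remainder: "All isolates not defined above will be assessed on a case-by-case basis via manual review by the Sponsor".

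**The concern.** Two kinds of decision are left to people: whether an isolate is a pathogen, and whether a deviation is important enough to remove a patient. Neither needs to know whether the patient responded, yet nothing in either document withholds that knowledge. Post-baseline pathogens cannot be determined without post-baseline cultures, so for cultures the review sees outcome data by its nature. No section separates the baseline calls from the post-baseline ones, or requires them to be dated and closed before outcomes are merged.

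In a single-arm study there is no control group in which such decisions could cancel. If patients who failed are more readily judged unevaluable, or their isolates are read differently, the reported rate moves. The non-susceptible group is the most sensitive because the sponsor expects only 40 such infections.

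**Working it through.** **Step 1: which decision reaches which rate.**

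| Decision | Rule or judgement | Reaches CE/ME | Reaches primary m-MITT |
|---|---|---|---|
| Important deviation (SAP 4.5(b), 7.9) | Clinical team, no criteria | Yes | No |
| Cure or failure assessed in window (4.5(c)) | Rule on post-baseline data | Yes | No |
| Other antibiotic (4.5(d)) | Sponsor manual review | Yes | No |
| Baseline pathogen, listed organism (6.4, Appendix 3) | Written rule | ME only | Yes, but by rule |
| Unlisted isolate alone (Appendix 3) | Sponsor, individually | No ME entry | No: cannot qualify a patient |
| Unlisted isolate beside a listed one | Sponsor, individually | ME | Possibly |
| Mixed infection with an organism outside the m-MITT limit | No attribution rule | ME | Possibly |
| Post-baseline pathogen call (4.7) | Sponsor, no written matching rule | ME | Numerator |

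Three points behind the table:

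- The two-species limit in SAP 4.4 counts species whether or not they are pathogens, so a sponsor call on an isolate cannot change it.
- Enterococci and *P. aeruginosa* always count as uropathogens under Appendix 3 but lie outside its m-MITT limit. The SAP does not say whether a woman with *E. coli* plus one of these is in or out. An unlisted co-isolate that is called a uropathogen raises the same question.
- Response in SAP 5.1 depends on Day 12 growth of the baseline uropathogen, so both the baseline and the Day 12 call feed it. All six sensitivity analyses in SAP 5.1.1 vary the symptom component; none varies the pathogen calls.

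**Step 2: the plan's own numbers.** Protocol 9.1 and SAP 6.1 expect 250 enrolled, 50 without a qualifying culture and 40 with a non-susceptible organism. They give no response rate, precision target or power, so there is no sample-size figure to reproduce.

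- Expected culture-positive: 250 − 50 = 200. This is an upper figure for m-MITT, since the species and organism limits can only reduce it, and ME is smaller still.
- Non-susceptible: 40/250 = 16%, or 40/200 = 20% if all 40 are in m-MITT.

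**Step 3: illustrative size.** Response rates and the number *k* of affected patients are assumptions. If *k* non-responders leave a denominator *n* with *r* responders, the rate becomes r/(n − k).

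| Group | k = 0 | Smaller k | Larger k |
|---|---|---|---|
| n = 200, assumed 70% | 140/200 = 70.0% | 140/198 = 70.7% (k = 2); 140/195 = 71.8% (k = 5) | 140/190 = 73.7% (k = 10) |
| n = 40, assumed 50% | 20/40 = 50.0% | 20/39 = 51.3% (k = 1); 20/38 = 52.6% (k = 2) | 20/36 = 55.6% (k = 4) |

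Over assumed rates of 50% to 80% with n = 200, the shift is +0.5 to +0.8 points (k = 2), +1.3 to +2.1 (k = 5) and +2.6 to +4.2 (k = 10). Removing responders moves the rate the other way: (140 − 5)/195 = 69.2%.

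Exact 95% intervals for comparison are 63.1% to 76.3% at 140/200 and 33.8% to 66.2% at 20/40.

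If a Day 12 call changes a patient's response instead of her membership, the shift is k/n: 5/200 = 2.5 points, or 2/40 = 5.0 points.

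**The case against.** A reader might infer that the primary denominator itself is open to case-by-case sponsor decisions made with outcomes in view. The documents do not support that.

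- SAP 4.7 states that m-MITT inclusion is programmatic, and SAP 6.4 supplies an ordered rule for the baseline pathogen and susceptibility.
- Individual sponsor assessment applies only to isolates on neither Appendix 3 list, and such an isolate alone cannot put a patient into m-MITT.
- Deviation and antibiotic exclusions act on CE, and through CE on ME. They never touch m-MITT.

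Nor would such decisions leave no trace. SAP 7.1 lists every patient's inclusion and exclusion with reasons, SAP 7.3 lists all isolates and whether each is considered pathogenic, and SAP 7.9 lists all deviations. SAP 5.3 also reports Day 12 overall response in ITT, whose membership needs no pathogen call.

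The sentence on concurrent review states timing only. That symptoms and rescue are visible to those deciding is an inference from the open-label design, the stated review of clinical data and the absence of any restriction. The shifts above assume that every removed patient is a non-responder, which is a worst case, and they fall inside the exact intervals. The study is descriptive (SAP 7.6), so no test is at risk.

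All of this stands, and it limits the point. What it leaves is that SAP 4.7 never says how sponsor pathogen determination fits with programmatic m-MITT inclusion, that the listings record decisions but are not said to show when they were made or what was then known, and that CE and ME depend openly on unrestricted judgement. A shift from selective decisions is also systematic, so sampling intervals do not cover it.

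**Conclusion.** The point holds in a limited form. CE and ME rates can depend on known response, because evaluability is partly a sponsor judgement made during an open-label study, without stated deviation criteria, blinding to response or a freeze. The primary m-MITT rate is exposed only through unlisted co-isolates, attribution of mixed infections under Appendix 3, and post-baseline pathogen calls.

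The documents do not say how many patients these routes could affect, and nothing shows that any decision was or would be biased. The percentages indicate possible size under assumed response rates and an assumed number of one-directional decisions; they are not estimates. The matter merits a change because the safeguard is cheap, not because a large bias has been shown.

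**What to change.** - **SAP 4.7 and Appendix 3.** State that m-MITT membership and susceptibility group follow only SAP 6.4 and Appendix 3, applied by program. Decide unlisted isolates and the attribution of mixed infections from a listing of baseline cultures only, without EOT or TOC cultures, symptoms or rescue. Date and freeze that listing before outcomes are merged.
- **SAP 4.5(b) and 7.9.** Decide deviation importance from the deviation text with response results removed, and sign off before database lock. The removal has to be deliberate, since deviations about visits or tests can disclose post-baseline information.
- **SAP 4.5(c) and post-baseline matching.** Apply both by program.
- **SAP 4.5(d).** Document the antibiotic review. It necessarily uses post-baseline data and cannot be made outcome-free.
- **Overrides.** List any manual override and show the primary result with and without it.

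The cost is one restricted listing and one sign-off, with no new data collection. The downside is the extra data-handling step.

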5 DEFINITION OF OUTCOME MEASURES

5.1 Primary Efficacy Outcome Measure

The primary efficacy outcome is overall response assessed on Day 12 (+/- 1 day) in the m-MITT using the definitions listed below.

A patient will be programmatically defined as a responder based on the following:

- The patient is alive;
- The patient has received no rescue therapy for uUTI (if an antibiotic active against the urinary tract pathogen is given for other reasons, then the patient will be considered indeterminate, and analyzed as a non-responder);
- The patient has resolution of the symptoms of uUTI present at trial entry and no new uUTI symptoms, on Day 12 (+/- 1 day);
- Urine culture taken on Day 12 (+/- 1 day) demonstrates <10³ CFU/mL of the baseline uropathogen;

A patient will be defined as a non-responder if at least one of the following criteria is met:

- The patient has died:
- The patient has received rescue therapy for uUTI (If an antibiotic active against the urinary tract pathogen is given for other reasons, then the patient will be considered indeterminate, and analyzed as a non-responder for uUTI);
- The patient has no resolution or worsening of the symptoms of uUTI present at trial entry and/or with new uUTI symptoms;
- Urine culture taken demonstrates $\geq 10^3$ CFU/mL of the baseline uropathogen;

All other patients will be considered indeterminate, including those with missing data needed to determine if the patient is a responder or non-responder. For example, if either urine culture or uUTI symptoms are not completed, the patient will be considered an indeterminate.

For the ITT and m-MITT populations, the proportion of ITT or m-MITT patients with a responder is defined using the following formula:

Number of responders

Number of responders + Number of non-responders + Number of indeterminates

By definition, patients in the CE and ME populations must have sufficient information for determination of efficacy response. Thus, the proportion of CE and ME patients is defined using the following formula:

Number of responders + Number of non-responders

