9.3 General Statistical Considerations

Descriptive statistics, including the numbers and percentages for categorical variables, and the numbers, means, standard deviations, medians, minimums, and maximums for continuous variables will be provided. Comparisons will be made between response rates for patients with infection due to ciprofloxacin-susceptible and ciprofloxacin-non-susceptible isolates. Exploratory analyses may also be performed. Listings of individual patient's data will be produced. A comprehensive Statistical Analysis Plan (SAP) will be finalized prior to final database lock.

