9.5.3 Analysis of Additional Efficacy Outcome Measures

The number and percentage of subjects treated with ciprofloxacin with an overall response of responder, non-responder, and indeterminate (by definition subjects with an indeterminate response are excluded the ME population) at the TOC visit will be presented for the m-MITT and ME-TOC populations.

Investigator determined clinical response (clinical cure, failure and indeterminate) at the Day 3 or 4 (+ 1 day) (EOT) and TOC Visits will be presented for the m-MITT, CE, and ME populations. The number and percentage of subjects with a microbiologic response of eradication, persistence, persistence with increasing MIC, and indeterminate (by definition subjects with an indeterminate response are excluded from the ME populations) will be presented for the following time points and analysis populations:

- Day 3 or 4 (+ 1 day) (EOT) in the m-MITT and ME-EOT populations
- Day 12 in the m-MITT and ME-Day12 populations

Overall response and microbiologic eradication at the EOT and TOC visits by baseline pathogen (key pathogens) will be summarized in the m-MITT and ME populations.

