4.1 Intent-to-Treat (ITT) Population

All enrolled patients regardless of whether or not they received ciprofloxacin.

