5.3 Additional Efficacy Outcomes Measures

Microbiologic response

Microbiologic response is assessed on Day 3 or 4 (+1 day) EOT and Day 12 (+/- 1 day) TOC in the ITT, m-MITT, CE-EOT, CE-TOC, ME-EOT and ME-TOC populations.

Microbiological	Definition
response	
Eradication	A urine culture taken at baseline and compared with the culture
	from the Day 3 (+1 day) (EOT) visit or Day 12 (+/- 1 day)
	(TOC) visit showed that the urine culture obtained at the
	relevant visit demonstrated <10 ³ CFU/mL of the original
	uropathogen.
Persistence	Uropathogen present at baseline grew at ≥10 ³ CFU/mL at the
	time-point of analysis, i.e. EOT or TOC.
Indeterminate	Patient was lost to follow-up or an assessment was not
	undertaken such that no urine culture was obtained (or culture
	results could not be interpreted for any reason) at either the
	EOT or the TOC visit.

• Clinical response:

Clinical response (done programmatically) will use the definitions below to document response at Day 3 or Day 4 (+ 1 day) (EOT), Day 12 (+/- 1 day) (TOC) and Day 21 in the ITT, m-MITT, CE-EOT, CE-TOC, ME-EOT and ME-TOC populations.

Clinical response	Definition
Clinical cure	All pre-therapy signs and symptoms of the index infection had resolved such that no additional antibiotics were required
Clinical failure	Patients who met any one of the criteria below were considered as failure:
	Death related to uUTI prior to Day 3 or Day 12 or Day 21 respectively
	No apparent response to treatment; persistence or progression of most or all pre-therapy signs and symptoms or use of additional antibiotics for the current infection
	Patient previously met criteria for failure and received rescue antibiotics
Indeterminate	Study data were not available for evaluation of efficacy for any reason, including:
	Patient lost to follow-up or assessment not undertaken such that a determination of clinical response could not be made at either the EOT or TOC visit
	Death prior to Day 3 or Day 12 or Day 21, respectively, where uUTI was clearly noncontributory

In addition to the clinical response above, following sensitivity analyses will be performed on Day 12 (+/- 1 day) in the m-MITT population,

- Sensitivity Analysis 1: Will follow the same definition of clinical response defined in section 5.3 except, urgency is excluded and considering all other symptoms are resolved and no new uUTI symptoms.

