- Overall response at Day 12 (+/- 1 day) (TOC) in the ITT, CE-TOC and ME-TOC population (m-MITT is used with the primary endpoint)
- Overall response, microbiologic response, clinical response and investigator response at the EOT and TOC visits by baseline pathogen (key pathogens) in the m-MITT and ME populations
- Overall response, microbiologic response and clinical response at the EOT and TOC visits by baseline ESBL in the m-MITT and ME populations
- Distribution of pathogens by culture concentration at EOT and TOC in the m-MITT, ME-EOT and ME-TOC populations

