8 DIFFERENCES WITH ANALYSES SPECIFIED IN THE PROTOCOL

- The clinical evaluability rules in the protocol have been modified in the SAP (section 4.5). The prior antibiotic rule was dropped because it is an exclusion criterion in the protocol and applicable to all patients. The requirement that a study entry urine culture obtained before ciprofloxacin administration was dropped since the clinical evaluability rules should only be related to clinical data, not microbiological data.
- The primary efficacy outcome measure in the SAP (section 5.1) was further clarified by adding the rules for non-responder.
- Analyses were added to the SAP (section 5.3) for day 21 even though they weren't listed in the protocol.
- The rule, 'patient previously met criteria for failure', in the protocol for clinical response was modified in the SAP (section 5.3) to 'patient previously met criteria for failure and received rescue antibiotics' to specify the rule more precisely.

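### SAP 5.3 extends overall and microbiologic response to ITT and CE, which do not require the baseline uropathogen these endpoints are scored against, and its clinical response classes omit partial responders

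*SAP*

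**What the plan says.** **Populations.** Protocol 9.5.3 reports overall response "at the TOC visit will be presented for the m-MITT and ME-TOC populations", and microbiologic response likewise in m-MITT and ME only. SAP 5.3 goes further. Microbiologic response is assessed at EOT and "TOC in the ITT, m-MITT, CE-EOT, CE-TOC, ME-EOT and ME-TOC populations", and overall response at Day 12 is reported "in the ITT, CE-TOC and ME-TOC population (m-MITT is used with the primary endpoint"). Overall response at EOT is also reported in ITT and CE-EOT.

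**Who is in them.** SAP 4.1 defines ITT as "All enrolled patients regardless of whether or not they received ciprofloxacin". SAP 4.5 draws CE from MITT and requires a determinate clinical response. The requirements for an interpretable culture and for eradication or persistence enter only with ME, in SAP 4.6.

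**Scoring.** The culture limb of overall response (SAP 5.1) and the eradication and persistence classes (SAP 5.3) all refer to the baseline or original uropathogen. SAP 5.1 sends everyone not otherwise classed to indeterminate. SAP 6.5 keeps indeterminates in the ITT and m-MITT denominators as failures. For CE and ME the SAP 5.1 denominator is responders plus non-responders, on the ground that "By definition, patients in the CE and ME populations must have sufficient information for determination of efficacy response".

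**Clinical response classes (SAP 5.3, programmatic).** Apart from the death and previous-failure rules, cure needs every pre-therapy symptom resolved. Failure needs no apparent response, most or all symptoms persisting or progressing, or additional antibiotics. Indeterminate needs unavailable data.

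**Section 8.** It records that "Analyses were added to the SAP (section 5.3) for day 21 even though they" were absent from the protocol. It has no entry for adding ITT and CE to these two endpoints. It explains the removal of the pre-treatment culture requirement from CE by saying that "the clinical evaluability rules should only be related to clinical data, not microbiological data".

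**The concern.** A patient with no baseline uropathogen cannot show that the drug cleared one. When she enters a table of overall or microbiologic response, her score reflects the absence of a pathogen and not the effect of ciprofloxacin. The study is descriptive (SAP 7.6), so the reported percentages are its result, and a reader will compare the ITT and CE rates with the m-MITT rate.

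The CE formula adds an asymmetry. A symptomatic patient without a pathogen meets a non-responder criterion and stays in the CE denominator. A symptom-free one is indeterminate, and the formula has no term for her.

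The gap in the clinical classes is a separate matter that reaches the same tables. CE criterion (c) requires cure or failure, and ME is built on CE. A patient who fits neither class has an undetermined place in both populations, although she is plainly not a responder under SAP 5.1.

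**Working it through.** **Inputs from the documents (SAP 6.1, Protocol 9.1).** 250 enrolled; 50 expected without at least 10^5 CFU/mL of a uropathogen; hence 250 − 50 = 200 with a qualifying culture. No response rate, alpha, power or precision is stated. Every rate below is an assumption, and ITT is taken as 250.

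**How many have no pathogen.** The 50 are patients below the threshold. Some may carry a low-count uropathogen that can be scored, since SAP 6.4 still yields a final baseline result for them. So 50 is an upper figure for this group; 40 and 25 are shown as well.

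**Step 1: ITT overall response under the SAP default.** With n patients without a pathogen, none of them can be a responder. The ceiling is (250 − n)/250. With a response rate p among the rest, the ITT rate is p(250 − n)/250.

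| n without a pathogen | Ceiling | ITT rate at assumed p = 70% |
|---|---|---|
| 50 | 200/250 = 80% | 140/250 = 56.0% |
| 40 | 210/250 = 84% | 147/250 = 58.8% |
| 25 | 225/250 = 90% | 157.5/250 = 63.0% |

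The same ceiling applies to ITT eradication. At an assumed 80% eradication and n = 50, the ITT figure is 160/250 = 64.0%.

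**Step 2: CE overall response under the SAP default.** Assume 200 CE patients: 160 with a pathogen, of whom 112 respond (112/160 = 70.0%), and 40 without. Symptom-free patients among the 40 drop out of the formula. The symptomatic ones, assumed to be clinical failures, remain as non-responders.

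| Symptom-free of 40 | Left as non-responders | CE rate |
|---|---|---|
| 24 | 16 | 112/176 = 63.6% |
| 32 | 8 | 112/168 = 66.7% |
| 36 | 4 | 112/164 = 68.3% |

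The CE microbiologic rate is not diluted if all 40 are dropped as indeterminate. There the problem is only that the stated ground for dropping them does not hold.

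**Step 3: does SAP 4.5 make the quoted statement true?** For clinical response in CE, yes, by criterion (c). For ME, yes, by SAP 4.6. For overall and microbiologic response in CE, no: none of criteria (a) to (d) requires a baseline uropathogen or an interpretable follow-up culture. The note to (c) uses the culture date for the visit window, so a patient with no culture may fall out in practice, but it does not ask for a usable result.

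**Step 4: partial responders.** Read most as more than half (an assumption). With complete data and no added antibiotic, the states that fit no class are 1 of 2, 1 of 3, 1–2 of 4 and 1–2 of 5 symptoms remaining.

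For ME overall response, take 160 patients and 112 responders. Keeping partial responders gives 112/160 = 70.0%. Dropping 8, 16 or 24 of them (5%, 10% or 15%) gives 112/152 = 73.7%, 112/144 = 77.8% or 112/136 = 82.4%.

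For a clinical cure rate, take 70% cured and 10% partial. The result is 70.0% if they are failures, 0.70/0.90 = 77.8% if dropped, and 80.0% if cures.

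**The case against.** **The SAP does give a default.** A reader might infer that pathogen-free patients are left unscored, or that having no pathogen satisfies the culture limb, so that a symptom-free patient is a responder. With n = 50, p = 70% and 60% to 90% symptom-free, that would give an ITT rate of 170/250 = 68.0% to 185/250 = 74.0%. The documents do not support resting the point on this. The SAP 5.1 catch-all and SAP 6.5 lead to indeterminate, and eradication compares baseline and later cultures for the original organism, which cannot be done when there was none. This objection stands. The difficulty lies in what the default does in ITT and CE.

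**Protocol 9.7 excludes patients with missing data from CE.** SAP 4.7 adds that the sponsor reviews microbiological as well as clinical data for CE inclusion. So it would be too strong to call the quoted statement baseless; it carries a protocol rule forward. But SAP 4.5 does not implement that rule for culture data, Section 8 argues the other way, and having no pathogen is not missing data.

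**The addition is permitted and partly visible.** Protocol 9.3 says "Exploratory analyses may also be performed". SAP 7.1 tabulates each population with a column for patients with no pathogen or a contaminated sample, and SAP 7.6 summarises reasons for indeterminate for most endpoints. A careful reader could undo much of the ITT dilution. That lowers the stakes but does not correct the percentages or supply the Section 8 entry.

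**Partial responders need not drop out.** A reader might infer that CE and ME rates are biased upward. That follows only if criterion (c) is read literally. Its parenthesis names only indeterminates, and the sensitivity analyses that replace resolution with improvement suggest a base rule of resolved versus not resolved. Classed as a failure or a cure, she stays in. The SAP does not say which, so a gap is established but a direction of bias is not.

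**Conclusion.** The point holds, at the level of a change that should be made. The ITT overall and microbiologic rates and the CE overall rate mix absence of a pathogen with drug effect. The only size that follows from the plan's own figures is the ITT ceiling of 80%, and it needs all 50 patients to have no pathogen; with fewer, the ceiling rises. The illustrated shifts, from 70.0% to 56.0–63.0% in ITT and to 63.6–68.3% in CE, rest on assumed response rates, assumed numbers without a pathogen and an assumed symptom-free share.

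The statement about sufficient information is sound for ME and for clinical response in CE, but not for overall or microbiologic response in CE. The clinical classes have a real gap whose effect depends on an unstated programming choice: none on ME overall response if partial responders are kept, a rise if they are dropped.

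A reader might carry any of this over to the main result. The documents do not support that: m-MITT requires a qualifying baseline culture, and SAP 5.1 scores symptoms by its own resolution rule. All the affected tables named here are additional outcomes. The investigator definition shares the partial-responder gap and feeds Sensitivity Analysis 6, but not the primary analysis itself.

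**What to change.** 1. In SAP 5.3, report overall and microbiologic response only in m-MITT and ME, or in those ITT and CE patients who have a baseline uropathogen. The second option keeps patients with scorable SAP Appendix 3 organisms that m-MITT leaves out. Keep ITT and CE in full for clinical and investigator response.
2. In SAP 5.1, limit the statement about sufficient information to ME and to clinical response in CE.
3. If a CE overall or microbiologic rate is kept, reconcile SAP 4.5 with Protocol 9.7 on missing culture data. Do not add indeterminates to the CE denominator, which would conflict with Protocol 9.7.
4. For the programmatic analysis classification only, and when symptom data are present, count any unresolved pre-therapy symptom, any new uUTI symptom or additional antibiotics for the infection as failure. This agrees with the symptom and rescue limbs of SAP 5.1 and keeps partial responders in CE and ME. Leave the SAP 5.3 death rules as they are.
5. List all of these in SAP Section 8, and note there that the investigator definition has the same gap.

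The cost is SAP wording; no new data are needed. CE and ME rates may be slightly less favourable, and the programmatic definition will depart from the investigator definition in Protocol 7.2.3.
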